We designed a four-week early OT intervention program for patients who have suffered a stroke with the aim of improving quality of life and facilitating their return home by providing them and their caregiver with knowledge about specific care and neurorehabilitation.

Specific Objectives

Primary outcome: Quality of life. Secondary results: Functional independence and support needs in activities of daily living, sensory-motor skills, perceptual-cognitive skills, communication skills, anxiety and depression levels.

Methods

Type and general design of the study

This is a prospective, randomized, controlled clinical trial. The population to be represented is that of patients who are discharged from the neurology service of the Virgen de la Victoria University Hospital (Malaga) and who, after medical discharge, are referred to the rehabilitation service of the Maritime Hospital of Torremolinos as outpatients by decision of the neurology and rehabilitation departments, but will not be inpatients in the Physical Medicine and Rehabilitation Unit for intensive rehabilitation.

Users who are referred to rehabilitation by obtaining a place as an inpatient, receive occupational therapy and physiotherapy daily for a period of maximum three months. However, patients who are referred to the rehabilitation service as an outpatient are taken home directly after discharge and are subsequently recalled for rehabilitation. The period that elapses from when they are discharged until they are called to begin their rehabilitation varies depending on the workload of the service, and can even be three months after discharge. Referral to external or intensive rehabilitation is made based on the rehabilitation potential, which takes into account certain criteria such as age, clinical situation and vascular injury existing at the time of discharge, social support, motivation and observed recovery. during admission. Patients assigned to the study program are included in an early occupational therapy intervention program and are compared with a control group that will receive usual care and rehabilitation.

Sample selection and size

The sample size "n" was calculated based on the main variable SAQOL-39 with the sample size determination formula for two independent groups, assuming a mean of 2.50, standard deviation of 0.75, significance level of 5%, a power of 80% and a critical difference of 0.54, obtaining a sample of 30 participants per group.

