Therefore, two groups were formed: an intervention group of 30 patients who will receive the early Occupational Therapy program in addition to the rehabilitation that they would receive independently of this study, and a control group of 30 patients who will receive the conventional rehabilitation.

Eligible patients were assigned to EOTIPS or the control group according to a pre-established computer randomized designation in blocks of six.

Inclusion and exclusion criteria

All patients must have diagnostic confirmation of stroke with single or multiple vascular lesions that had occurred in the same time period, demonstrated by neuroimaging tests (CT or MRI), be over 18 years of age, go home on discharge and live within a maximum of 30 minutes away from the hospital center, with >2 or <26 points on the National Institute of Health scale (NIHSS), 30–100 points on the Barthel Index (BI) on the second day after the stroke (with BI 100, the patient

can be included if the Montreal Cognitive Assessment is <26) and having been referred to the rehabilitation service as an outpatient. Inclusion in the study occurs prior to hospital discharge, within a two- week interval after the stroke.

Exclusion criteria are: NIHSS > 26, BI < 30, and life expectancy < 1 year. Also excluded are people with a previous stroke, dementia or other types of diseases that cause dementia and other neurological, psychiatric or medical diseases (for example, severe epilepsy, traumatic brain injury, schizophrenia, COPD, severe or unstable heart disease, sleep apnea) concomitants that could alter cognitive function, presence of moderate or severe aphasia, people who do not understand Spanish or English, as well as patients who have been referred to the Physical Medicine and Rehabilitation Unit as inpatients to receive intensive rehabilitation or who are discharged to a care home.

The variables will take into account: age, sex, educational level, marital status, nationality, mother tongue, employment, vascular territory and lesion volume.

List of results and evaluations

Patient evaluations	
Quality of life	- SAQOL-39
Level of functional independence	- BI - mRS - SIS-16
Perceptual-cognitive skills	- MoCA
Sensory-motor skills	Fugl MeyerBergTime up & go
Communication skills	- CAL
Anxiety and/or depression levels	- Berg - Hamilton

Assessments to be used in the study (all translated into Spanish)

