The rehabilitation and neurology departments were responsible for referring patients to the occupational therapist and including them in the study. Before starting rehabilitation, the occupational therapist and her family explored the patient's needs and desires and decide individual goals for the intervention period.

Occupational Therapy intervention during the discharge process. The intervention has a person-centered approach that is based on who the user is: their context, their history, their family members, their individual strengths and weaknesses. Individualized objectives will be established, taking into account the patient's potential and limitations. Examples of goals could be: being able to wash independently, hanging clothes or riding the bus, or how to manage bills. OT intervention may involve training in different activities or thinking about different ways to adapt to difficult situations to achieve a goal. For example, for some patients the intervention may consist of carrying out

ADLs in which they have a limitation with the support of the occupational therapist with the aim of enhancing their sense of security during its performance. Data will be collected through note taking and analyzed with qualitative content analysis.

The designed OT intervention includes:

- Prior to discharge: Initial evaluation and a hospital session.
- Post-discharge: A two-hour home visit, telephone follow-up, a one-hour visit one month after discharge and final evaluation three months later.

This early OT intervention will be carried out independently of the usual care of the rehabilitation service of the Torremolinos Maritime Hospital.

Time planning

The project will begin in January 2021 and was estimated to last one year and three months (estimated completion in March 2022). Finally, the project was completed on November 2022.

Day 1: Hospital (1 hour)					
Initial interview and evaluation.					
Day 2: Hospital (1 hour)					
Information about stroke. Postural care.					
Day 3: Home (2 hours)					
Environment assessment, equipment and					
recommendations and establishment of					
individualized objectives.					
Day 4 - day 29: PHONE FOLLOW-UP.					
Implementation of the rehabilitation by the patient					
and caregiver (individual objectives).					
Day 30: Home (1 hours).					
Final assessment of individualized objectives at					
home.					
After 3 months: Home (1 hour)					
Final evaluation.					

Results analysis plan

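### A single fixed block size of six with no described concealment leaves up to a quarter of assignments predictable by the departments that select and include patients

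*Combined protocol and SAP*

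**What the plan says.** All references are to the combined protocol and SAP.

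- **Sample selection and size.** Patients were assigned "according to a pre-established computer randomized designation in blocks of six". The arms are "an intervention group of 30 patients who will receive the early Occupational Therapy program" and "a control group of 30 patients who will receive the conventional rehabilitation". The ratio is not stated in words, but 30 and 30 imply 1:1, so three and three in each of ten blocks. No second block size is mentioned.
- **Type and general design of the study.** Patients come from one hospital's neurology service and go to rehabilitation "as outpatients by decision of the neurology and rehabilitation departments". On how that decision is reached: "Referral to external or intensive rehabilitation is made based on the rehabilitation potential". The considerations listed include motivation, social support and the recovery seen in hospital.
- **Inclusion and exclusion criteria.** Outpatient referral is itself a condition of entry, and inclusion happens before discharge.
- **Hospital discharge planning.** "The rehabilitation and neurology departments were responsible for referring patients to the occupational therapist and including them in the study".
- **Occupational Therapy intervention during the discharge process.** The programme begins in hospital: "Prior to discharge: Initial evaluation and a hospital session".

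The text does not say who held the list, when each assignment was released, whether it was concealed, or whether anyone was masked.

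**The concern.** Four features occur together: one fixed block size, eligibility that depends on judgement about prognosis, the same departments controlling both eligibility and entry, and a therapy session on the ward before discharge that could reveal earlier assignments. If recruiters can work out the next assignment, a patient with good prospects can be offered or held back to suit the expected arm. The arms would then differ at entry.

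The repeated-measures ANOVA uses the baseline measurement, but it would only partly remove such a difference, because prospects such as motivation or family support are not fully captured by a baseline score. The primary outcome is a quality-of-life scale and the trial has 60 patients, so a modest tilt could produce or hide an apparent effect. The limitations section foresees arms that differ in severity and puts this down to chance. Steering would look the same, and the plan offers no means of telling the two apart.

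**Working it through.** **The plan's own figure.** The plan gives no predictability figure. Its sample size supplies the scale for what follows: SD 0.75, difference 0.54, 5% significance (taken as two-sided), 80% power.

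2 × [0.75 × (1.960 + 0.842) / 0.54]² = 30.28 per group, against 30 stated. Power at 30 is 79.6% by the normal approximation. The stated size is reproduced to within rounding, and nothing here turns on it.

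**Predictability of a block of six (3 + 3).** There are 20 equally likely orderings. An assignment is certain once one arm has used its three places.

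| Certain assignments in the block | Orderings |
|---|---|
| 3 | 2 |
| 2 | 6 |
| 1 | 12 |

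- Mean: (3×2 + 2×6 + 1×12) / 20 = 30/20 = 1.5 of 6, or 25%. Over ten blocks this is 15 of 60.
- By position, the 4th assignment is certain in 10% of blocks, the 5th in 40% and the 6th always: 0.10 + 0.40 + 1.00 = 1.5.
- Guessing the arm with more places left is right for 4.1 of 6 assignments, or 68.3%, against 50% by chance.

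These figures require knowledge of the block size, the block boundaries and every earlier assignment. With less knowledge the certain share falls, down to zero.

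**Possible bias.** Suppose staff steer only when certain, raising prognosis by *s* when the next patient will be in one arm and lowering it by *s* when in the other. Bias in the difference = 2 × 0.25 × *s*. The documents give no value for *s*, so a range is assumed.

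- *s* = 0.10: 2 × 0.25 × 0.10 = 0.05, and 0.05/0.54 = 9%.
- *s* = 0.25: 2 × 0.25 × 0.25 = 0.125, and 0.125/0.54 = 23%.

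**Type I error.** Standard error = 0.75 × √(2/30) = 0.194.

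- Bias 0.05: 0.05/0.194 = 0.26. P(Z > 1.70) + P(Z < −2.22) = 0.044 + 0.013 = about 6%.
- Bias 0.125: 0.125/0.194 = 0.65. P(Z > 1.31) + P(Z < −2.61) = 0.094 + 0.005 = about 10%.

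**Effect of mixing block sizes.** In simulated lists of 60 with sizes 4, 6 and 8 equally likely, and an observer who knows the set of sizes but not their order, the certain share falls to about 2%. The best-guess rate *g* stays near 68%. What this buys depends on behaviour (shown for *s* = 0.25):

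| Steering | Formula | Fixed six | Mixed 4/6/8 |
|---|---|---|---|
| Only when certain | 2 × certain share × *s* | 0.125 | about 0.01 |
| On every best guess | 2 × *s* × (2*g* − 1) | 2 × 0.25 × 0.367 = 0.183 | 2 × 0.25 × 0.356 = 0.178 |

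Mixing sizes removes certainty but hardly touches steering on probable guesses. Only control over when the assignment is released deals with both.

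**The case against.** The strongest reply is that fixed blocks of six do no harm if allocation is concealed, so the gap may be one of reporting. Much of that stands. Three stronger readings are tempting, and the documents do not support them.

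- **That recruiters knew a quarter of the assignments.** A reader might infer this from the arithmetic. Nothing shows that the departments knew the block size or kept a tally. The arm-specific hospital contact is a single one-hour session, and both arms were evaluated before discharge, so being seen in hospital does not by itself reveal the arm. The rehabilitation service is at a different hospital. Earlier assignments were observable in principle, and no more than that is shown.
- **That the block size was available to recruiters because the protocol prints it.** The time-planning section reports completion in November 2022, so the text was edited after the trial ended. It does not show what staff could read during enrolment. That the trial was open is likewise an inference, from the nature of the intervention and the absence of any masking statement.
- **That baseline was taken after assignment was known.** The initial evaluation is listed within the therapy programme, but the evaluation section places it in both arms, after consent and before discharge. Its order relative to assignment is unstated.

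It is also fair that the prognosis shift is assumed, and that a completed trial cannot change its list. None of this supplies the missing description of concealment, which is what would settle whether the upper bound applied.

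**Conclusion.** The point holds as a design weakness with an upper bound attached, and is not evidence that selection bias occurred. At most 25% of assignments (15 of 60) were certain and about 68% guessable, given full knowledge of block size, boundaries and history. The documents neither show that knowledge nor describe anything that would prevent it.

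The bias of 0.05 to 0.125 points, and the type I error of about 6% to 10%, rest on an assumed shift of 0.10 to 0.25 SAQOL-39 points, steering in opposite directions for the two arms at every certain position and nowhere else, and the plan's SD of 0.75. The true shift may be zero. Without a statement of who held the list and when each assignment was released, a reader cannot tell where in this range the trial lies.

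**What to change.** **In the plan's wording.** Replace the fixed size of six with randomly mixed block sizes (for example 4, 6 and 8) that are not disclosed to the referring departments or the treating therapist. State who holds the list. Release each assignment only after consent, the outpatient-referral decision and the baseline evaluation are recorded. The release rule is the more important part.

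**For the completed trial.**

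1. Report who held the list, and how and when each assignment was released.
2. From the retained list and enrolment order, compare baseline SAQOL-39 and NIHSS by predicted next assignment.
3. Repeat the primary comparison without the fully determined positions, as a sensitivity analysis only.

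**Cost.** Mixed sizes are a setting when the list is generated; the final split may miss 30/30 by a few patients. The retrospective work is a short analysis of data the trial should hold. Its limits should be stated. Dropping the determined positions leaves about 45 patients. At 22.5 per arm the standard error is 0.75 × √(2/22.5) = 0.224 and 0.54/0.224 = 2.41, so power is Φ(2.41 − 1.96), about 67% against 79.6% with all 60. The analysis also does not remove steering on uncertain guesses, so an unremarkable result would not rule out selection.

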The following analysis model was followed: to study the differences that may exist between one group and another, before and after the intervention, a repeated measures ANOVA was carried out; to check how some variables influence others, a multivariate analysis was carried out and, finally, to know the mean and normal distribution of the variables, descriptive statistics were performed. An intragroup analysis was included by performing paired T-test studies along with Wilcolxon for non-parametric measurements. The program used for data analysis was JAMOVI (version 2.3.26).

Difficulties and limitations of the study

Regarding the limitations of this study, it is worth highlighting the biases possibly derived from the adherence to treatment of the users and their caregivers, as well as the behavior and involvement of the family member in the process that will likely induce differences in the results. It is worth highlighting the importance of the word of the patient and the caregiver due to the telephone process of the intervention, since it can lead to differences in the instructions provided by the occupational therapist and, therefore, in the treatment and final result.

Furthermore, an important limitation is the heterogeneity of the sample, since we are generally talking about patients who have had a stroke of any location, extent and volume. The random distribution of patients may result in the two groups having significant differences in the severity of their injuries or their potential for recovery. Also due to the heterogeneity of each patient's rehabilitation process, it is understood that, of the total sample size, certain patients will subsequently receive a greater number of conventional rehabilitation sessions than others, and some patients will probably not even receive any sessions. This is why it seems

interesting to subsequently study the care received by each user three months after discharge, as well as their level of functionality and quality of life.

Ethical considerations

During data collection, the anonymity of users was guaranteed. Participants will be informed of the intervention and will be asked to sign an informed consent, with participation being voluntary and allowing the user to abandon whenever they wish.

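### NIHSS is required for entry, yet neither it nor stroke type is a listed variable, and the SAQOL-39 comparison names no severity covariate although the plan names severity imbalance as a limitation

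*Combined protocol and SAP*

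**What the plan says.** All places are in the combined protocol and SAP.

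- **Inclusion and exclusion criteria.** Entry depends on stroke severity, "with >2 or <26 points on the National Institute of Health scale (NIHSS", and the exclusions repeat it: "Exclusion criteria are: NIHSS > 26, BI < 30, and life expectancy < 1 year". Stroke is to be confirmed by imaging, "demonstrated by neuroimaging tests (CT or MRI". The section ends with the variable list: "The variables will take into account: age, sex, educational level, marital status, nationality, mother tongue, employment, vascular territory and lesion volume". NIHSS and stroke type are not in it. Lesion volume is, with no measurement method.
- **List of results and evaluations**, and the instrument descriptions after it. These cover SAQOL-39, BI, mRS, SIS-16, MoCA, Fugl-Meyer, Berg, TUG and CAL, among others, assessed in both arms before discharge and at three months. NIHSS is not among them.
- **Sample selection and size.** Patients are allocated "according to a pre-established computer randomized designation in blocks of six". No stratification is stated.
- **Results analysis plan.** The arms are compared before and after the intervention by repeated measures ANOVA. A multivariate analysis of how variables influence one another is also mentioned. No covariate is named for either.
- **Difficulties and limitations of the study.** Sample heterogeneity is called an important limitation: "The random distribution of patients may result in the two groups having significant differences in the severity of their injuries".

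**The concern.** The plan identifies a threat, holds a standard measure of it for every patient, and does not commit to reporting or using that measure. Blocks of six keep the arm sizes equal but do nothing to balance severity.

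Two things are at stake. First, a reader of the results could not see from the planned variables whether the arms were alike on the severity score that governed entry, or in their mix of stroke types. Second, if the arms did differ, no prespecified analysis would take it into account. An adjustment chosen afterwards from the many baseline scales would invite the question of why that scale was picked.

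**Working it through.** **Inputs from the plan:** SD 0.75, difference 0.54, 5% significance, 80% power, 30 per group (Sample selection and size). Two-sided testing is assumed because the plan does not say.

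**Input not in the plan:** the correlation r between NIHSS and SAQOL-39. It is taken as 0.3 to 0.5, in absolute value, as an assumption.

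**1. The plan's own figure.** n per group = 2 × (0.75 × (1.960 + 0.842) / 0.54)² = 30.28, or 31 rounded up. The stated 30 is reproduced to within one patient. Power at 30 per group is 79.6% (normal approximation) or 78.3% (t test). Nothing here is in dispute.

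**2. Size of a chance imbalance.** The arm difference in any one baseline factor, in SD units, has standard deviation √(2/30) = 0.258.

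| Imbalance | z | Two-sided probability |
|---|---|---|
| ≥ 0.25 SD | 0.25 / 0.258 = 0.97 | 33% |
| ≥ 0.5 SD | 0.5 / 0.258 = 1.94 | 5% |

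The median absolute imbalance is 0.6745 × 0.258 = 0.174 SD.

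**3. Effect on an unadjusted three-month difference.** Shift = r × imbalance × 0.75.

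| Imbalance | r = 0.3 | r = 0.5 | Share of 0.54 |
|---|---|---|---|
| 0.5 SD | 0.11 | 0.19 | 21% to 35% |
| 0.174 SD (median) | 0.04 | 0.07 | 7% to 12% |

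**4. Effect on the planned before-after comparison.** With two arms and two time points, the group-by-time term compares mean change. If the SD is 0.75 at both times, the shift is (r at three months − r at baseline) × imbalance × 0.75. With equal correlations it is zero. With 0.3 at baseline and 0.5 at three months, a 0.5 SD imbalance gives 0.2 × 0.5 × 0.75 = 0.075, or 14% of 0.54. What matters is how far NIHSS predicts change in SAQOL-39, and the documents give no figure for that.

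**5. Precision from adjustment.** Adjusting a three-month comparison for a covariate with correlation r multiplies the residual SD by √(1 − r²). At r = 0.3 the SD is 0.75 × 0.954 = 0.72 and power at 30 per group is 83%. At r = 0.5 it is 0.75 × 0.866 = 0.65 and power is 90%. These compare with 79.6% unadjusted. Once baseline SAQOL-39 is in the model, the further gain from NIHSS would depend on what NIHSS adds to it.

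**The case against.** The strongest reply is that the plan already has good means of looking at severity. BI, mRS, SIS-16, Fugl-Meyer, Berg, TUG and MoCA are assessed in both arms before discharge, and the before-after analysis uses each patient's baseline SAQOL-39. Chance imbalance under randomisation is also not a bias in the usual sense: it is already within the standard error of the unadjusted difference, 0.75 × 0.258 = 0.19. The 0.5 SD case is uncommon, and the shift in step 3 belongs to an analysis that the plan does not propose. All of this stands, and it limits the point to a missing adjustment and a missing report.

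A reader might infer more, and the documents do not support it:

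- **That severity imbalance cannot be examined.** The baseline scales allow a comparison, and NIHSS scores obtained for eligibility could still be tabulated.
- **That the multivariate analysis rests on lesion volume as its only severity marker.** The variable list is not said to be exhaustive or tied to a model, and the multivariate analysis names no variables.
- **That CT and MRI volumes are pooled.** The mention of CT or MRI concerns confirming the diagnosis. How lesion volume is obtained is not stated.
- **That the mortality contrast in the introduction shows stroke type to be prognostic here.** Those figures (up to 50% for haemorrhagic, 25% for ischaemic) are acute-phase deaths. The trial enrols patients who are going home and measures quality of life at three months.

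The reply does not close the gap. Holding baseline scales is not the same as a planned adjustment, none of them is named as a severity covariate, and a comparison of change does not remove a difference in recovery that severity predicts.

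**Conclusion.** The point holds as an improvement worth making; no figure in the plan is shown to be wrong. NIHSS governs entry but is neither a listed variable nor a covariate, stroke type is not listed, and the planned SAQOL-39 comparison does not adjust for the imbalance that the plan itself raises.

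The size is moderate and conditional. An imbalance of 0.5 SD or more has about a 5% chance. With r assumed at 0.3 to 0.5, a 0.5 SD imbalance would move an unadjusted three-month difference by about a fifth to a third of the 0.54 target. In the planned before-after comparison the effect would be smaller if NIHSS relates similarly to SAQOL-39 at both times, and could be nil. The case for acting rests as much on the low cost and the likely gain in precision as on the risk of a misleading result.

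**What to change.** - **Inclusion and exclusion criteria.** Add entry NIHSS and stroke type to the variable list, and report both by arm. State when NIHSS is scored: the text fixes the second day after the stroke for BI, and it is unclear whether this also covers NIHSS, while inclusion may occur up to two weeks after the event.
- **Results analysis plan.** Add a between-arm analysis of three-month SAQOL-39 adjusted for baseline SAQOL-39 and entry NIHSS. The plan reports the project as completed in November 2022, so if the data have already been analysed, label this analysis as added after completion.
- **Lesion volume.** It need not be reduced to descriptive use. A sentence on how it was measured would help the reader.

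The cost is a wording change and one or two model degrees of freedom. With 60 patients, residual degrees of freedom go from 60 − 2 = 58 in a plain two-arm comparison to 60 − 4 = 56 with both covariates. No new data collection is needed, because NIHSS and imaging are already required for entry.
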